10.8 Recurrence-Free Survival

Recurrence-Free Survival: From date of registration to the first documentation of recurrence (as defined in [Section 10.5](#)). Patients last known to be alive and not to have recurred are censored at the date of last contact.

10.9 Cancer-Specific Survival

Cancer-Specific Survival: From date of registration to date of death due to bladder cancer. Patients without bladder cancer death are censored at last contact date or date of non-bladder cancer death.

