1.2 Secondary Objective(s)

- a. To estimate event-free survival at 18 months for the subset of patients with papillary cancer (Ta/T1).
- b. To estimate progression-free survival, cystectomy-free survival, bladder cancer-specific survival, overall survival in all patients.

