- f. All patients with T1 urothelial carcinoma at study entry must undergo re-TURBT within 60 days prior to registration, and must have evidence of uninvolved muscularis propria in the pathologic specimen from either the first or the second TURBT. Tissue from the re-resection must be submitted for central review in addition to the tissue from the first TURBT (see [Section 12.0](#)). The TURBT that identified the recurrent T1 disease may have taken place more than 60 days prior to registration but not more than 120 days. Patients with high grade Ta or CIS do not require a re-TURBT, but if this is performed at the discretion of the treating physician, the second TURBT must be within 60 days of registration. There is no requirement for muscularis propria in the specimen of Ta/CIS patients, but the tissue from the first and second TURBTs must be submitted for central review. If a patient with Ta/T1 disease undergoes repeat TURBT, the patient will be stratified as having CIS if there is CIS on either TURBT.
- g. Patients must not have had urothelial carcinoma in the prostatic urethra within the previous 24 months or muscle invasive urothelial carcinoma of the bladder at any time. Patients with prior urothelial carcinoma in the upper urinary tract within the previous 24 months will only be eligible if they had \leq T1 carcinoma and were treated with nephroureterectomy. Patients must have a CT or MRI (including CT-

IVP, CT-urogram or MR-urogram) of the abdomen and pelvis to rule out upper tract malignancy and intra-abdominal metastases within 90 days prior to registration. If a patient cannot tolerate intravenous contrast, a retrograde pyelogram should be performed within 90 days prior to registration.

- h. Patients must be deemed unfit for radical cystectomy by the treating physician, or the patient must refuse radical cystectomy, which is considered standard of care for these patients. The reason for patients not to undergo cystectomy will be clearly documented.

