5.4 Clinical/Laboratory Criteria

- a. Patients must be ≥ 18 years of age.
- b. Patients must have adequate bone marrow function as evidenced by all of the following: ANC $\geq 1,500$ / microliter (m μ L); platelets $\geq 100,000$ /m μ L; Hemoglobin ≥ 9 g/dL. These results must be obtained within 42 days prior to registration.
- c. Patients must have adequate hepatic function as evidenced by the following: total bilirubin ≤ 1.5 x institutional upper limit of normal (IULN) (except Gilbert's Syndrome, who must have a total bilirubin < 3.0 mg/dL), and AST or ALT ≤ 2 x IULN. These results must be obtained within 42 days prior to registration.
- d. Patients must have adequate renal function as evidenced by ONE of the following: serum creatinine ≤ 1.5 ULN OR measured or calculated creatinine clearance ≥ 30 mL/min. This result must have been obtained within 42 days prior to registration.

$$\text{Estimated creatinine clearance} = \frac{(140 - \text{age}) \times \text{wt (kg)} \times 0.85 \text{ (if female)}}{72 \times \text{creatinine (mg/dl)}}$$

- e. Patients must have Zubrod Performance Status ≤ 2 (see [Section 10.11](#)).
- f. Patients must have a baseline ECG performed within 42 days prior to registration.
- g. Patient must not have history of idiopathic pulmonary fibrosis, pneumonitis (including drug induced), organizing pneumonia (i.e., bronchiolitis obliterans, cryptogenic organizing pneumonia, etc.), or evidence of active pneumonitis.
- h. Patients must not have an active infection requiring oral or IV antibiotics within 14 days prior to registration. Patients receiving prophylactic antibiotics (e.g., for prevention of a urinary tract infection or chronic obstructive pulmonary disease) are eligible.
- i. Patients must not have severe infections within 28 days prior to registration, including but not limited to hospitalization for complications of infection, bacteremia, or severe pneumonia.

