7.7 Follow-Up Period

All patients will be followed for recurrence, progression, and survival for 5 years after registration.

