11.0 STATISTICAL CONSIDERATIONS

11.1 Patient Populations

Eligible patients are defined as registered patients who met all the pre-registration eligibility criteria listed in Section 5 that were in effect at the time of the 12/14/18 amendment. The determination of eligibility regarding Disease Related Criteria will be based on local pathology review.

Evaluable patients are defined as registered patients who received any amount of study drug (atezolizumab).

Efficacy analyses will be based on patients who are determined to be both eligible and evaluable as defined above.

Safety analyses will be based on patients who are determined to be evaluable as defined above. Patients who are registered in the study but who do not receive any study drug will not be included in safety analyses.

11.2 Estimate of Sample Size:

A sample size of 135 eligible patients (evaluable) will be enrolled over 36 months with 18 months of additional follow-up. Our goal is to enroll 70 patients with a CIS component and 65 patients with Ta or T1 disease only. One stratum may be closed prior to accrual completion to ensure adequate patient numbers in both disease groups. An additional 50% will be enrolled to account for ineligibility or initial treatment refusal resulting in a total sample size of 202. With Revision #5 (Version Date 12/14/18) a pre-registration Study Chair approval form was enacted which has significantly reduced the rate of ineligible registrations.

11.3 Analysis:

There will be two co-primary aims for this study: The first objective to be tested involves the complete response rate in the subset of patients with CIS (see [Section 10.1](#)). The second co-primary objective involves event-free survival at 18 months for all evaluable patients. A hierarchical approach will be used to test the two co-primary aims. The CIS aim will be tested first. Only if the result is statistically significant will the second primary objective be evaluated. Only patients who received at least one dose of atezolizumab per protocol will be evaluable for these two primary objectives. Both co-primary tests will be conducted at the one-sided 0.05 significance level.

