A secondary aim of interest is the assessment of EFS in the Ta/T1 subset. With n=65 eligible and evaluable patients, there will be 71% power to detect Ho: 20% vs. Ha: 30%, using a one-sided alpha=0.05. Other secondary estimates and confidence intervals of endpoints of progression-free survival (PFS), cystectomy-free survival, bladder cancer specific survival (CSS) and overall survival (OS) will also be provided using Kaplan-Meier estimation. Short-term estimates at 18 months and long-term estimates at 5 years for these secondary endpoints will be of interest. Qualitative and quantitative toxicity assessment will be provided using CTCAE reporting. CR and adverse event rates can be estimated to within $\pm 9\%$ (95% confidence interval). A toxicity with a true incidence of 1% (5%) has a 69% (99%) chance of being observed at least once in this single arm trial.

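### Cancer-specific survival is estimated only by Kaplan-Meier with other-cause deaths censored; a cumulative incidence of bladder-cancer death should be added for absolute risk

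*Combined protocol and SAP*

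**What the plan says.** Section 1.2 of the protocol lists the endpoint among the secondary objectives: "To estimate progression-free survival, cystectomy-free survival, bladder cancer-specific survival, overall survival in all patients". Section 10.9 measures it from registration to death from bladder cancer and adds that "Patients without bladder cancer death are censored at last contact date or date of non-bladder cancer death".

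Section 11.3 names the estimator: "bladder cancer specific survival (CSS) and overall survival (OS) will also be provided using Kaplan-Meier estimation", with confidence intervals. It also sets the time points: "Short-term estimates at 18 months and long-term estimates at 5 years for these secondary endpoints will be of interest". Section 7.7 supports the later one: "All patients will be followed for recurrence, progression, and survival for 5 years after registration".

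Neither Section 10 nor Section 11 mentions a cumulative incidence function or any other competing-risk method for this endpoint. Neither says how the Kaplan-Meier figure is to be interpreted.

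**The concern.** A patient who has died of another cause can no longer die of bladder cancer. Censoring that patient makes Kaplan-Meier treat the remaining risk as if it were still open, at the rate seen in those still alive. One minus the estimate then describes a hypothetical setting in which other causes of death do not operate, and even that reading needs the two causes to be independent. It is not the proportion of enrolled patients who will die of bladder cancer.

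The eligibility criteria suggest that other-cause deaths will occur. Under Section 5.2h, "Patients must be deemed unfit for radical cystectomy by the treating physician, or the patient must refuse radical cystectomy", and Section 5.4e allows Zubrod status up to 2. The follow-up is long enough for these deaths to accumulate.

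At stake is how a secondary 5-year figure is read. A clinician who takes its complement as absolute risk would take it as too high. The figure would also not fit with overall survival, which is reported beside it.

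**Working it through.** The documents state no rate, precision or power for cancer-specific survival, so there is no figure of the plan to reproduce. The check compares the planned estimator with the cumulative incidence.

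**Inputs from the protocol.** Censoring rule (Section 10.9); Kaplan-Meier at 18 months and 5 years (Section 11.3); 135 eligible and evaluable patients (Section 11.2).

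**Assumptions, not in the documents.** Constant, independent hazards h_b (bladder cancer) and h_o (other causes). Five-year net bladder-cancer death of 10-20%. Five-year net other-cause death of 20-40%.

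**Formulas.** A net 5-year risk p gives a hazard h = -ln(1 - p)/5. At time T in years:

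- complement of the planned Kaplan-Meier: 1 - exp(-h_b T)
- cumulative incidence: [h_b/(h_b + h_o)] × [1 - exp(-(h_b + h_o)T)]

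**Lowest corner, 10% and 20%, 5 years.** -ln 0.9 = 0.1054 and -ln 0.8 = 0.2231. Cumulative incidence = 0.1054/(0.1054 + 0.2231) × (1 - 0.9 × 0.8) = 0.321 × 0.28 = 9.0%. The gap is 10.0 - 9.0 = 1.0 point.

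**Highest corner, 20% and 40%, 5 years.** -ln 0.8 = 0.2231 and -ln 0.6 = 0.5108. Cumulative incidence = 0.2231/0.7340 × (1 - 0.8 × 0.6) = 0.304 × 0.52 = 15.8%. The gap is 20.0 - 15.8 = 4.2 points.

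| Net bladder / other-cause, 5 years | 1 - KM, 5 years | Cumulative incidence, 5 years | Gap (relative) | Gap, 18 months |
|---|---|---|---|---|
| 10% / 20% | 10.0% | 9.0% | 1.0 (11%) | 0.1 |
| 10% / 40% | 10.0% | 7.9% | 2.1 (27%) | 0.2 |
| 15% / 30% | 15.0% | 12.7% | 2.3 (18%) | 0.2 |
| 20% / 20% | 20.0% | 18.0% | 2.0 (11%) | 0.2 |
| 20% / 30% | 20.0% | 16.9% | 3.1 (18%) | 0.3 |
| 20% / 40% | 20.0% | 15.8% | 4.2 (27%) | 0.5 |

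Gaps are in percentage points.

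**Simulation check.** For 20% and 30%, with 135 patients followed for 5 years and 4,000 runs, the mean of 1 - KM was 20.0% and the mean Aalen-Johansen estimate was 16.9%. The standard deviation of the Kaplan-Meier estimate was 3.7 points, so the 3.1-point gap is a little under one standard error.

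**Rough anchor from the documents.** Section 2.0 gives 30-40% progression to muscle-invasive disease in high-risk patients and about 50% bladder-cancer death at 10 years after progression. Multiplying gives 15-20% at 10 years. With a constant hazard, the 5-year figures are 1 - √0.85 = 7.8% and 1 - √0.80 = 10.6%. With other-cause death of 20-40%, the gap runs from 7.8 - 7.0 = 0.8 points to 10.6 - 8.3 = 2.3 points. The anchor therefore points to the lower part of the assumed range.

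**Fit with overall survival.** In the 20% / 30% case, all-cause death is 1 - 0.8 × 0.7 = 44%. Subtracting the Kaplan-Meier complement leaves 44 - 20 = 24% for other causes, whereas the actual share is 44 - 16.9 = 27.1%.

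**The case against.** The strongest reply is that the plan is coherent as written. It defines the endpoint with an explicit censoring rule and names the matching estimator, which together give net cause-specific survival. The plan nowhere says it will report one minus Kaplan-Meier as bladder-cancer mortality. This stands: preferring cumulative incidence is a choice of estimand, and the gap is an error only if the complement is read as absolute risk. What remains is that the plan neither states the net interpretation nor offers a summary for the absolute-risk reading.

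A reader might also infer that competing mortality is heavy in this trial. The documents do not support that. They give no age distribution and no other-cause death rate, and no split between unfit patients and those who refuse surgery. Fit patients who refuse cystectomy are eligible, and Zubrod 2 is a ceiling. Sections 5.4b-d and 5.4i-o require adequate organ function and exclude several serious conditions, which pulls the other way.

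Nor is the plan's question the risk of bladder-cancer death with the bladder kept. Section 1.2 asks for cancer-specific survival in all patients, and Section 10.9 does not censor at cystectomy.

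Finally, the endpoint is for estimation only, in a single-arm trial, and overall survival is reported with it. That also stands, and it limits the weight of the point.

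**Conclusion.** The point holds as a minor improvement to a secondary endpoint. The direction is certain: with any other-cause deaths, the complement of the planned estimate exceeds the actual probability of bladder-cancer death. The size is not known from the documents. Over the assumed ranges, with constant independent hazards, it is about 1.0 to 4.2 points at 5 years (11% to 27% relative) and about 0.1 to 0.5 points at 18 months, where it can be ignored. That other-cause deaths will be non-trivial by 5 years is a reasonable inference from eligibility, not a documented rate. A reader might conclude that the planned analysis is invalid or that the trial's main conclusions are at risk. Neither follows, since net survival is a legitimate estimand and no primary test, interim rule or sample size uses this endpoint.

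**What to change.** Keep the definition in Section 10.9 and label it there as net (cause-specific) survival. Add one sentence to Section 11.3: the cumulative incidence of bladder-cancer death will be estimated by the Aalen-Johansen method at 18 months and 5 years, with confidence intervals and with death from other causes as a competing event.

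The cost is that sentence and one standard procedure. Cause of death is already needed for the existing definition, and Section 14.4n already requires a Notice of Death. No visits, data collection or patient numbers change.

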10.10 Overall Survival

Overall Survival: From date of registration to date of death due to any cause. Patients last known to be alive are censored at the date of last contact.

10.11 Performance Status

Performance Status: Patients will be graded according to the Zubrod Performance Status Scale.

POINT	DESCRIPTION
0	Fully active, able to carry on all pre-disease performance without restriction.
1	Restricted in physically strenuous activity but ambulatory and able to carry out work of a light or sedentary nature, e.g., light housework, office work.
2	Ambulatory and capable of self-care but unable to carry out any work activities; up and about more than 50% of waking hours.
3	Capable of limited self-care, confined to bed or chair more than 50% of waking hours.
4	Completely disabled; cannot carry on any self-care; totally confined to bed or chair.

11.0 STATISTICAL CONSIDERATIONS

11.1 Patient Populations

Eligible patients are defined as registered patients who met all the pre-registration eligibility criteria listed in Section 5 that were in effect at the time of the 12/14/18 amendment. The determination of eligibility regarding Disease Related Criteria will be based on local pathology review.

Evaluable patients are defined as registered patients who received any amount of study drug (atezolizumab).

Efficacy analyses will be based on patients who are determined to be both eligible and evaluable as defined above.

Safety analyses will be based on patients who are determined to be evaluable as defined above. Patients who are registered in the study but who do not receive any study drug will not be included in safety analyses.

11.2 Estimate of Sample Size:

A sample size of 135 eligible patients (evaluable) will be enrolled over 36 months with 18 months of additional follow-up. Our goal is to enroll 70 patients with a CIS component and 65 patients with Ta or T1 disease only. One stratum may be closed prior to accrual completion to ensure adequate patient numbers in both disease groups. An additional 50% will be enrolled to account for ineligibility or initial treatment refusal resulting in a total sample size of 202. With Revision #5 (Version Date 12/14/18) a pre-registration Study Chair approval form was enacted which has significantly reduced the rate of ineligible registrations.

11.3 Analysis:

There will be two co-primary aims for this study: The first objective to be tested involves the complete response rate in the subset of patients with CIS (see [Section 10.1](#)). The second co-primary objective involves event-free survival at 18 months for all evaluable patients. A hierarchical approach will be used to test the two co-primary aims. The CIS aim will be tested first. Only if the result is statistically significant will the second primary objective be evaluated. Only patients who received at least one dose of atezolizumab per protocol will be evaluable for these two primary objectives. Both co-primary tests will be conducted at the one-sided 0.05 significance level.

The first primary objective is the estimation of the CR rate in the subset of patients with CIS. Enrollment of 70 eligible and evaluable patients with a CIS component will be ensured. If the total number of patients out of 70 who respond is 28 (40%) or greater, the agent would be considered promising. This design has a significance level (probability of falsely declaring that an agent with a 30% complete response probability is worthy of further investigation) of 4.6%, and a power (probability of correctly declaring than an agent with a complete response rate of 50% is worthy of further investigation) of 96%. Seventy evaluable patients are sufficient to estimate the CR rate at 25 weeks (± 1 week) to within $\pm 12\%$ (95% confidence interval). Those CIS patients without a biopsy at 25 weeks will be assumed to be non-responders. Duration of CR is defined as the time from date of biopsy documenting the complete response to the time of first high-grade recurrence, and is a key additional secondary endpoint. With a CR rate of 50%, we would expect 35 patients would have a CR. We can estimate the proportion still in CR at 18 months to within $\pm 17\%$ (95% confidence interval).

One interim futility assessment will be made in the CIS subset. We will evaluate the first 25 eligible and evaluable CIS patients for pathologic response at 25 weeks. Since accrual is expected to be slow, accrual will continue while the interim evaluation is underway. A favorable evaluation would be if 7 or more CRs are seen in the first 25 eligible and evaluable CIS patients. This is equivalent to testing the alternative hypothesis of a 50% complete response rate at the one-sided $\alpha=0.02$. If results are favorable, accrual will continue to a total of 70 eligible and evaluable CIS patients.

The second primary endpoint is event-free survival (EFS) (as defined in [Section 10.0](#)) at 18 months in the mixed population of patients with either CIS or Ta or T1 disease. This objective will only be tested if the null hypothesis in the first co-primary objective is rejected as specified above. The 18-month EFS estimate will be obtained using the method of Kaplan and Meier, and the Greenwood formula will be used to estimate the variance. A 90% confidence interval will be estimated for the 18-month EFS estimate. If the lower 90% confidence bound excludes 20%, the investigators will conclude the regimen significantly improves EFS relative to historical trial data.

Based on published rates (see table below), it is assumed that if the true 18-month EFS rate in this mixed patient population is $\leq 20\%$, then this regimen will not warrant further investigation in this setting, whereas a 30% or greater EFS rate at 18 months would be of

considerable interest. This study has a type I error rate (one-sided) of 0.05 and statistical power of 0.93.

There will be one interim analysis conducted at the end of accrual. The 99% confidence interval around the 18 month EFS Kaplan-Meier estimate will be constructed. If the upper confidence bound rules out 30% then consideration will be given to reporting the results early due to futility. There is no adjustment to the alpha for this interim test because it is based on futility. We will not consider reporting early due to efficacy. Because one of the primary endpoints occurs at 18 months and accrual is expected to be steady but modest, an interim analysis of EFS prior to this point in the trial will not be informative.

There are several trials with outcomes that can be used as historical controls for this trial. Most of these are described in [Section 2.0](#).

Drug	Study	Patients	Outcome
Valrubicin	Steinberg 2000	BCG-unresponsive CIS	21% @ 3 mo 17% @ 12 mo 8% @ 24 mo
Valrubicin	Dinney 2013	BCG-unresponsive CIS	10% @ 12 mo 3% @ 24 mo
Gemcitabine	Skinner 2013	mostly BCG unresponsive CIS/Ta/T1 (89% high grade)	28% @ 12 mo 20% @ 24 mo
Gemcitabine	DiLorenzo 2010	mix of BCG failure/unresponsive	19% @ 24 mo
Docetaxel	Lamont 2005	mix of BCG failure/unresponsive	40% @ 12 mo 25% @ 36 mo
MCNA	Morales 2015	mix of BCG failure/unresponsive	20.9% @ 12 mo (FDA analysis)
rAdIFN	Dinney 2015	BCG unresponsive CIS/Ta/T1	35% @ 1 mo

Only Valrubicin is FDA approved in this setting, and is therefore the most representative historic control. Compared to all of these studies, our intended endpoint of 30% EFS at 18 months would demonstrate a clear improvement in outcome.

A secondary aim of interest is the assessment of EFS in the Ta/T1 subset. With n=65 eligible and evaluable patients, there will be 71% power to detect Ho: 20% vs. Ha: 30%, using a one-sided alpha=0.05. Other secondary estimates and confidence intervals of endpoints of progression-free survival (PFS), cystectomy-free survival, bladder cancer specific survival (CSS) and overall survival (OS) will also be provided using Kaplan-Meier estimation. Short-term estimates at 18 months and long-term estimates at 5 years for these secondary endpoints will be of interest. Qualitative and quantitative toxicity assessment will be provided using CTCAE reporting. CR and adverse event rates can be estimated to within $\pm 9\%$ (95% confidence interval). A toxicity with a true incidence of 1% (5%) has a 69% (99%) chance of being observed at least once in this single arm trial.

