5.0 ELIGIBILITY CRITERIA

Each of the criteria in the following section must be met in order for a patient to be considered eligible for registration. Use the spaces provided to confirm a patient's eligibility. For each criterion requiring test results and dates, please record this information on the Onstudy Form and submit via Medidata Rave® (see [Section 14.0](#)). Any potential eligibility issues should be addressed to the SWOG Statistics and Data Management Center in Seattle at [name] or [contact] prior to registration.

In calculating days of tests and measurements, the day a test or measurement is done is considered Day 0. Therefore, if a test is done on a Monday, the Monday 3 weeks later would be considered Day 21. This allows for efficient patient scheduling without exceeding the guidelines. If Day 21 or 42 falls on a weekend or holiday, the limit may be extended to the next working day.

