5.1 Study Chair Approval Requirement

Patients' disease related criteria ([Section 5.2](#)) and BCG-unresponsiveness ([Section 5.3a](#)) must be discussed with at least one of the **S1605** Study Chairs prior to registration. The **S1605** Pre-Registration Study Chair Approval form must be signed by one of the **S1605** Study Chairs to indicate approval within 30 days prior to registration.

The **S1605** Pre-Registration Study Chair Approval Form is located in [Section 18.4](#). See [Section 14.4a](#) for form submission requirements.

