- Ψ For all patients with CIS at study entry, one urine cytology slide is required for central pathology review. See [Section 12.0](#) for instructions.
- Θ Baseline histology used to diagnose disease for eligibility (from biopsy or TURBT), per [Section 5.1a](#).
- λ Baseline labs (except TSH) to be obtained within a window of 3 weeks.

Allowable windows

Treatment must begin within 7 calendar days of registration.

Allowable windows for scheduled disease assessments performed every 12 weeks is +/- 14 days, every 24 weeks is +/- 14 days. The window is to be calculated from the scheduled date of the procedure/assessment.

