1. Baseline collection, submitted within 7 days after registration. All tissue obtained within 60 days prior to registration for histologic confirmation of recurrent disease (see [Section 5.1](#)). For T1 patients, tissue from the prestudy re-resection and original TURBT (even if > 60 days prior to registration) must be submitted.
2. All subsequent biopsies for suspected recurrence including negative biopsies and those that show any recurrence (high or low grade).
3. FOR PATIENTS WITH CIS DISEASE AT STUDY ENTRY: Within 28 days after Week 25 biopsy.

Urine Cytology

1. FOR PATIENTS WITH CIS DISEASE AT STUDY ENTRY: Within 28 days after Week 13 and Week 25 disease assessments.

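### Does fixing eligibility at the 12/14/18 criteria shut earlier registrants out of the efficacy set, and do Sections 11.3 and 12.1 define a different set?

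*Combined protocol and SAP*

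**What the plan says.** Section 11.1 (Patient Populations) sets the efficacy population in two steps. Eligible patients are those who "met all the pre-registration eligibility criteria listed in Section 5 that were in effect at the time of the 12/14/18 amendment". Evaluable patients are those who received any amount of atezolizumab. Efficacy analyses use patients who are both. On the pathology source 11.1 is direct: "The determination of eligibility regarding Disease Related Criteria will be based on local pathology review".

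Section 5.0 opens by saying "Each of the criteria in the following section must be met in order for a patient to be considered eligible for registration". Section 5.1 follows. It requires discussion with a Study Chair and a form signed by one of the "Study Chairs to indicate approval within 30 days prior to registration". Section 11.2 dates this step: "With Revision #5 (Version Date 12/14/18) a pre-registration Study Chair approval form was enacted". It adds that the form has markedly lowered the rate of ineligible registrations. On numbers, 11.2 targets 135 eligible and evaluable patients and says "An additional 50% will be enrolled to account for ineligibility or initial treatment refusal resulting in a total sample size of 202".

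Two other places use different words:

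- **Section 12.1a** says central pathology review will confirm the diagnosis and settle eligibility. Sections 15.0 and 18.2 call it an eligibility review.
- **Section 11.3** introduces the EFS objective as covering all evaluable patients. It also describes evaluable as at least one dose given per protocol.

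**The concern.** Three features together suggest that the denominator of both co-primary tests is not fixed.

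1. The date that freezes the criteria in 11.1 is the date of the revision that introduced the Study Chair form. The form requirement sits inside Section 5, and 5.0 makes every item there a condition of eligibility. No sentence exempts patients registered earlier, so a literal reader would remove all of them.
2. Sections 11.1 and 12.1a name different pathology readers for eligibility. Under 12.1a, central review is not completed before treatment starts. If it governed, patients would be excluded after treatment had begun.
3. If the EFS set were all evaluable patients, treated but ineligible patients would enter it. The plan allows for up to 202 registrations against an efficacy set of 135, so that difference could be large.

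The complete response (CR) test uses a fixed count, 28 of 70, so a change of denominator would change its error rates. A population settled only once outcomes are known is the kind of discretion that pre-specification is meant to remove.

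**Working it through.** **The plan's own figures**

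*Registrations (11.2).* 135 × 1.5 = 202.5, stated as 202. The implied share entering the efficacy set is 135/202 = 66.8%.

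*CR rule (11.3).* Inputs: success if at least 28 of 70 respond; continue at the interim if at least 7 of the first 25 respond; null rate 30%, alternative 50%. The exact binomial with both conditions gives alpha 0.0464 and power 0.960. The plan states 4.6% and 96%.

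*EFS (11.3).* Inputs: 18-month EFS of 20% against 30%, one-sided 0.05, 36 months of accrual and 18 months of follow-up. Under an exponential model:

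- λ0 = −ln(0.20)/18 = 0.0894 and λ1 = −ln(0.30)/18 = 0.0669, so ln(λ0/λ1) = 0.290.
- P(event) under λ1 = 1 − (e^(−18λ1) − e^(−54λ1))/(36λ1) = 1 − (0.300 − 0.027)/2.408 = 0.887.
- Expected events d = N × 0.887, and power = Φ(0.290·√d − 1.645).

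| N | Expected events | Power | Plan states |
|---|---|---|---|
| 65 | 57.6 | 0.712 | 71% (Ta/T1 subset) |
| 135 | 119.7 | 0.937 | 0.93 (all patients) |
| 202 | 179.1 | 0.987 | none |

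This is the only variant tried that comes close to both stated powers. Binomial, normal, arcsine and log-log versions give 0.55 to 0.64 at N = 65 and 0.81 to 0.90 at N = 135. It is used here only to identify the N behind the stated power.

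**Which set does 11.3 mean?**

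The CR paragraph of 11.3 speaks of 70 eligible and evaluable CIS patients. The secondary-aim paragraph of 11.3 speaks of 65 eligible and evaluable Ta/T1 patients for EFS. 70 + 65 = 135, the target in 11.2, and 135 is the N that fits the stated EFS power. The shorter phrase about evaluable patients is therefore a loose reference to the set in 11.1. The two descriptions of evaluable, any amount of drug and one dose per protocol, differ mainly for a partial or deviating first infusion. Section 11.1 says efficacy uses the terms as it defines them.

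**Does the missing form make early patients ineligible?**

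- Section 11.2 compares the rate of ineligible registrations before and after the form. If lacking the form made a patient ineligible, the earlier rate would be 100% by definition and the comparison would mean nothing.
- Section 5.1 is headed a requirement, whereas 5.2 to 5.6 are headed criteria. It asks that 5.2 and 5.3a be discussed with a Study Chair. The form in 18.4 records the dates and findings needed to check those sections. It verifies substantive criteria and does not describe the patient.
- The footnote in 9.1 on "Baseline histology used to diagnose disease for eligibility (from biopsy or TURBT" cites 5.1a, and 12.1e on "All tissue obtained within 60 days prior to registration for histologic confirmation of recurrent disease" cites 5.1. Both subjects now sit in 5.2. This fits the approval step having been placed in front of the disease criteria later, with the cross-references left unrevised. It does not show when.
- The text in hand is later than the date named in 11.1, since Section 14.4 refers to Revision #9 of 09/20/2021. Section 11.2 dates the form, but does not say where in the protocol it then stood.

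**Which pathology reading decides eligibility?**

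Section 11.1 names local review. Section 18.3 matches it in practice: data coordinators check each eligibility criterion and confirm pathology from the report uploaded to the data system. Sections 10.1 and 10.5 use the local reading for CR and recurrence, and 12.1a itself uses it for decisions on continuing treatment. Objective 1.3a treats local-central agreement on recurrence and CR as a quantity to estimate. Sections 15.0 and 18.2 deal with specimen handling.

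**The case for a change.** The best case for a change is that an exemption nobody wrote down is still not in the plan. Section 14.1 says inadequately documented patients are generally deemed ineligible, and Section 18.3 has coordinators work through every criterion. A strict coordinator could fail an early registrant on 5.1. Section 12.1a says expressly that the local reading governs treatment continuation, but has no matching sentence for eligibility.

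The CR rule also has little slack. With the cut-off held at 28, alpha is 0.055 at n = 71 and 0.065 at n = 72, and power is 0.951 at n = 69 and 0.940 at n = 68. Clarifying sentences would cost little. An all-treated sensitivity analysis could use data that 14.1 already requires on ineligible patients.

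The textual part stands: the three inconsistencies are real. The numerical part does not carry the point. Those figures show what happens to any fixed cut-off when the achieved n misses the planned n, and none of the three slips is shown to cause such a miss. An all-treated analysis would resolve none of the wording questions, and the 28-of-70 rule has no stated counterpart at another n. It remains available as a descriptive supplement.

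**Conclusion.** No change is needed. The efficacy set is fixed by 11.1: eligible on the substantive Section 5 criteria, judged by local pathology, with any amount of atezolizumab received. The planned counts agree with it (70 + 65 = 135), and an analyst who follows it reaches a sound population for both co-primary tests. What remains is clerical: an unstated exemption for patients registered before the form existed, a stray reference to eligibility in 12.1a, and a shortened phrase in 11.3.

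No stated figure is shown to be wrong. The CR rule's 4.6% and 96% are reproduced at 0.0464 and 0.960, and the EFS power of 0.93 is matched closely at 0.937 with N = 135. The effect of the rejected readings cannot be sized, because the documents give neither the number registered before 12/14/18 nor the local-central discordance rate on eligibility.

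The conclusion rests on two readings: that 5.1 is a registration check on 5.2 and 5.3a, as the comparison in 11.2 implies, and that the explicit population rule in 11.1 prevails over passing descriptions elsewhere.
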